Prior or concomitant medication review #	X		х	X		Х	Х	х		X	Any use of prohibited concomitant medications (see Section 6.5.4), will be reviewed by the investigator and/or the sponsor, who will determine if the participant should be discontinued from the study.
AE review #	(===									-	
Vital signs (RR, height, and weight) #	X							X		X	Height measurement will not be performed at Visit 6 or Early Termination visit.
Vital signs (blood pressure, pulse rate, and temperature) #	X			X		X	X	X		X	
Physical examination #	X							X		X	

Study Day																																					
Unless otherwise specified with a '#', all	Visit 1 Screening																												Visit 2		sit 3 eline)	Visit 4	Visit 5		it 6 xit)	Early Termination	Notes
examinations/procedures for a timepoint will be	up to 1 before	4 days Visit 2	Day -14 (± 2)	Da	y 1	Day 14 (± 2)	Day 28 (± 3)		y 42 (5)	NA																											
performed in the order listed below*	Pre- CAE	Post- CAE	NA	Pre- CAE	Post- CAE	NA	NA	Pre- CAE	Post- CAE	NA																											
12-lead ECG [#]	X							х	х	Х	ECGs will be performed in approximately 20% of all participants. ECGs will be conducted at selected sites only. For more information, see Section 8.1.7. At Visit 6, ECGs will be performed at 0 hour (predose) and at 45 ± 15 minutes postdose.																										
Pregnancy test (WOCBP only)#	х			X				х		х	Serum pregnancy test will be performed at Screening visit; at all other indicated visits serum or urine pregnancy test will be performed.																										
Drugs of abuse screen #	X			X							Breathalyzer may be used for alcohol.																										
Hematology, chemistry, and urinalysis #	X			X			X	X		X																											
Serology #	X				·																																

Study Day						Interven	tion Period	 I			
Unless otherwise specified with a '#', all	Visit 1 Screening		Visit 2		sit 3 seline)	Visit 4	Visit 5	Vis	it 6 xit)	Early Termination	Notes
examinations/procedures for a timepoint will be	up to 1 before	14 days Visit 2	Day -14 (± 2)	Da	ay 1	Day 14 (± 2)	Day 28 (± 3)	Day	y 42 (5)	NA	
performed in the order listed below*	Pre- CAE	Post- CAE	NA	Pre- CAE	Post- CAE	NA	NA	Pre- CAE	Post- CAE	NA	
Manifest refraction	X							X		X	
Best-corrected visual acuity	X		X	X		X	X	X		X	
Slit lamp biomicroscopy	X	X	X	X	X	X	X	X	X	X	

Study Day											
Unless otherwise specified with a '#', all	Visit 1 Screening		Visit 2	visit 3 (Baseline)		Visit 4	Visit 5		it 6 xit)	Early Termination	Notes

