examinations/procedures for a timepoint will be	up to 1 before	4 days Visit 2	Day -14 (± 2)	Da	y 1	Day 14 (± 2)	Day 28 (± 3)		y 42 (5)	NA	
performed in the order listed below*	Pre- CAE	Post- CAE	NA	Pre- CAE	Post- CAE	NA	NA	Pre- CAE	Post- CAE	NA	
Blood sample collection for PK analysis				X	X	X	X	X	X	X	Blood samples for PK analysis will be collected at time 0 hour (predose) and prior to CAE entry (where applicable) at Visits 3, 4, 5, and 6. In addition, samples will be collected at 0.5 hour postdose, after CAE exposure on Visits 3 and 6. At the Early Termination visit, only a single sample will be collected. For the full blood sampling schedule, refer to Table 8-13.
Tear sample collection for PK analysis				x	x	x	x	x	x		Tear samples for PK analysis will be collected at time 0 hour (predose) prior to CAE entry (where applicable) on Visits 3, 4, 5, and 6. In addition, samples will be collected at 0.5 hour postdose, after CAE exposure on Visits 3 and 6. See Section 8.4.3. Not performed at the Early Termination visit if a participant is discontinued due to the use of prohibited medication.

Study Day		Intervention Period									
Unless otherwise specified with a '#', all	before Visit 2				Visit 3 (Baseline)		Visit 5	Visit 6 (Exit)		Early Termination	Notes
examinations/procedures for a timepoint will be			Day -14 (± 2)	Day 1		Visit 4 Day 14 (± 2)	Day 28 (± 3)	Day 42 (± 5)		NA	
performed in the order listed below*	Pre- CAE	Post- CAE	NA	Pre- CAE	Post- CAE	NA	NA	Pre- CAE	Post- CAE	NA	
CAE exposure	x				х			х			Not performed at the Early Termination visit if a participant is discontinued due to the use of prohibited medication.
Randomization					X						

Study Day			Intervention Period								
Unless otherwise specified with a '#', all	Visit 1 Screening		Visit 2	Visit 3 (Baseline)		Visit 4	Visit 5	Visit 6 (Exit)		Early Termination	Notes
examinations/procedures for a timepoint will be	up to 14 days before Visit 2		Day -14 (± 2)	Day 1		Day 14 (± 2)	Day 28 (± 3)	Day 42 (± 5)		NA	
performed in the order listed below*	Pre- CAE	Post- CAE	NA	Pre- CAE	Post- CAE	NA	NA	Pre- CAE	Post- CAE	NA	

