Administration of study intervention			x		x	X	X		х		Assigned study intervention will be administered as a single drop to both eyes, twice daily (approximately 12 hours apart) on Days -14 to 41, followed by a single dose administration to both eyes on Day 42. The morning dose will be administered by site staff on visit days. Not performed at the Early Termination visit if a participant is discontinued due to the use of prohibited medication.
Drop Tolerability Questionnaire					х	х	х		Х		Drop Tolerability Questionnaire will commence 5 (± 1) minutes following morning administration of study intervention. Not administered at the Early Termination visit if a participant is discontinued due to the use of prohibited medication.

Study Day			Intervention Period								
Unless otherwise specified with a '#', all examinations/procedures for a timepoint will be	Visit 1 Screening		Visit 2	Visit 3 (Baseline)		Visit 4	Visit 5	Visit 6 (Exit)		Early Termination	Notes
	up to 14 days before Visit 2		Day -14 (± 2)	Day 1		Day 14 (± 2)	Day 28 (± 3)	Day 42 (± 5)		NA	
performed in the order listed below*	Pre- CAE	Post- CAE	NA	Pre- CAE	Post- CAE	NA	NA	Pre- CAE	Post- CAE	NA	
Dispensing of the study intervention to participant			X		X	X	X				
Collection of used and unused study intervention					Х	х	х		х	Х	If necessary, to facilitate participant flow at the site on any given day, collection of used and unused study intervention can be done upon arrival of participants.
Intraocular pressure		X							X	X	
Dilated fundus exam		X							X	X	
Study exit									X	X	

AE = adverse events; CAE = controlled adverse environment; ECG = electrocardiogram; NA = not applicable;
RR = respiration rate;
WOCBP = women of child bearing potential

[;] PK = pharmacokinetic;

After completion of Informed Consent and Inclusion/Exclusion Criteria, for assessments listed with a '#' flexibility in procedure order is allowed,

2. Introduction

[figure not shown]
This study is the first-in-human (FIH) evaluation of the safety, tolerability, pharmacokinetics (PK), and exploratory efficacy of 2 novel interventions, AGN-242428 and AGN-231868, applied through topical ocular instillation. Both compounds are being developed for the treatment of the signs and symptoms of dry eye disease (DED).

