6.5.4. Prohibited Interventions During the Study

The decision to administer a prohibited intervention is done with the safety of the study participant as the primary consideration. When possible, Allergan must be notified before the prohibited intervention is administered. Use of the following interventions is prohibited during the study:

Stage 1:

- Use of ophthalmic prescription or OTC eye medications (eye drops, gels, or ointments) or artificial tear products as outlined in the exclusion criteria
- Corticosteroids administered through any route
- Systemic immunomodulators (eg, hydroxychloroquine, methotrexate, cyclosporine)
- Cyclosporine administered through any route
- Medications associated with the treatment of severe DED and/or Meibomian gland disease (eg, oral antimuscarinics, cevimeline, oral macrolides, tetracyclines, tetracycline derivatives, and retinoids)
- Xiidra (lifitegrast ophthalmic solution, 5%)
- TrueTear
- Contact lens wear in either eye
- Punctal or intracanalicular plugs
- Lid-heating therapy (ie, LipiFlow, iLUX, etc.), Meibomian gland probing, or therapeutic Meibomian gland expression
- Systemic medications, which may affect DED or vision (antihistamines, cholinergic
 agents, anticholinergics, beta blocking agents, tricyclic antidepressants and
 phenothiazines) unless the start date is > 7 days prior to the Screening visit and the
 dosing regimen is not changed during the study
- Hormone replacement therapy, oral or transdermal contraception, estrogen, progesterone, or other medications required for long-term treatment unless the start date is > 7 days prior to the Screening visit and the dosing regimen is not changed during the study
- Androgen therapy unless the start date is > 7 days prior to the Screening visit and the dosing regimen is not changed during the study
- Inhalable or ingestible cannabis products or transdermal patches containing THC

Stage 2:

- Systemic immunomodulators (eg, hydroxychloroquine, methotrexate, cyclosporine)
- Cyclosporine administered through any route
- · Corticosteroids administered through any route
- Medications associated with the treatment of severe DED and/or Meibomian gland disease (eg, oral antimuscarinics, cevimeline, oral macrolides, tetracyclines, tetracycline derivatives, and retinoids)
- Xiidra (lifitegrast ophthalmic solution, 5%), with the exception of those participants who
 are randomized to the Xiidra intervention arm
- TrueTear
- Contact lens wear in either eye

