7.2. Participant Discontinuation/Withdrawal from the Study

- A participant may withdraw from the study at any time at his/her own request or may be withdrawn at any time at the discretion of the investigator for safety, behavioral, compliance, or administrative reasons.
- Participants may be discontinued at the discretion of the investigator and/or the sponsor if they use any prohibited treatments described in Section 6.5.4.
- For participants who discontinue from the study early, every effort must be made to have these participants return to the clinical center for completion of the Early Termination visit. AEs leading to participant early discontinuation must be followed-up as appropriate.
- If the participant withdraws consent for disclosure of future information, the sponsor may retain and continue to use any data collected before such a withdrawal of consent.
- See the SoA (Section 1.3) for data to be collected at the time of study discontinuation (Early Termination). If the Early Termination visit falls on the same day as another scheduled visit, only Early Termination visit assessments will be conducted.
- Study termination

The dosing of study intervention may be paused due to safety concerns at any time by the site investigator. The sponsor and DMC must be notified immediately if the dosing was paused.

The sponsor may stop the study (and/or the study site) for any reason with appropriate notification.

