9.3. Populations for Analyses

The analysis populations will consist of participants as defined in Table 9-1.

Table 9-1 Analysis Populations

Population	Definition
Intent-to-Treat (ITT) (Stage 2)	All randomized participants in Stage 2. Participants will be summarized according to the randomized study intervention.
Pharmacokinetic (Stage 1)	All participants who have evaluable PK parameters in Stage 1
Pharmacokinetic (Stage 2)	All participants with available plasma or tear concentrations in Stage 2
Safety (Stages 1 and 2)	All participants who received ≥ 1 administration of study intervention for the stage
Biomarker (Stages 1 and 2)	All participants who have evaluable tear biomarker samples for the stage

Exploratory efficacy analyses will be performed on ITT population. PK analyses will be performed on PK population. Safety analyses will be performed on safety population.

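### Stage 2 allows removal from the whole study for prohibited-medication use, so later safety and Day 42 data can be lost selectively from randomized participants

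*Protocol*

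**What the plan says.** The Stage 2 Schedule of Activities (protocol Table 1-2, note on medication review) says that prohibited-medication use "will be reviewed by the investigator and/or the sponsor, who will determine if the participant should be discontinued from the study". Protocol Section 7.2 has the same rule: "Participants may be discontinued at the discretion of the investigator and/or the sponsor if they use any prohibited treatments described in Section 6.5.4". Neither place gives criteria for the decision. Safety withdrawal by the investigator is a separate item in Section 7.2.

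The Stage 2 list in Section 6.5.4 includes corticosteroids and cyclosporine by any route and "Medications associated with the treatment of severe DED and/or Meibomian gland disease". It also includes contact lenses, cannabis products and changes to hormone therapy. The same section says: "The decision to administer a prohibited intervention is done with the safety of the study participant as the primary consideration". Section 6.5.3 states that rescue medicine does not apply.

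On follow-up, Sections 7.1 and 7.2 foresee an Early Termination (ET) visit. The visible text provides no scheduled visits after it. Under Section 4.4, the last visit before discontinuation counts as the ET visit. Section 8.2.1 collects adverse events up to Exit or ET, and Section 9.4.2.1 does not count later ones as treatment-emergent.

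On analysis, Section 9.3 says: "Exploratory efficacy analyses will be performed on ITT population". That population is everyone randomized in Stage 2. Evaluation of safety and tolerability is the primary objective.

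**The concern.** Two decisions are joined here that are better kept apart: whether a participant has used a drug that complicates interpretation, and whether the participant stays under observation. The amendment summary gives the reason for the discretion as judging whether a medication is likely to affect the results. Removal on that ground protects the interpretation of the data, and its price is missing data.

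The missingness need not be neutral. A participant given a corticosteroid for an inflamed eye, or a drug for severe dry eye disease, is probably doing worse than average or is being treated for an adverse event. If that participant is removed, the safety record stops early for someone informative about safety, and the Day 42 outcome of a randomized participant is never observed. The decision is also made case by case after the event. Section 6.3.2 itself warns that knowledge of adverse events can suggest the assignment and bias assessments.

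At stake are the descriptive safety profile over six weeks in a first-in-human ocular study and the exploratory estimates meant to cover all randomized participants.

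**Working it through.** The plan states no power, effect size, SD, dropout rate or rate of prohibited-medication use (Sections 9.1 and 9.2), so there is no figure of its own to reproduce on this point. The planned counts agree: 5 × 50 = 250 in Stage 2.

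**Step 1: what removal costs under Table 1-2.** Compare the examinations still scheduled with the single ET set.

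- *Removed between Day 1 and Day 14.* Acuity and slit lamp: 3 visits remain (Days 14, 28, 42), ET supplies 1, net loss 2. Laboratory tests: 2 remain (Days 28, 42), ET supplies 1, net loss 1.
- *Removed between Day 14 and Day 28.* Acuity, slit lamp and laboratory tests: 2 remain, ET supplies 1, net loss 1.
- *Removed after Day 28.* One visit remains and ET replaces it, but earlier than planned.
- *Intraocular pressure and dilated fundus examination.* After baseline these are scheduled only at Day 42 and at ET, so no Day 28 measurement exists to lose. ET replaces the exit measurement, at an earlier time.
- *In every case.* New non-serious adverse events after ET and the Day 42 outcomes, with and without the CAE, are not collected.

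For CAE exposure and tear sampling the notes say: "Not performed at the Early Termination visit if a participant is discontinued due to the use of prohibited medication". For the Drop Tolerability Questionnaire, part of the primary endpoint, they say: "Not administered at the Early Termination visit if a participant is discontinued due to the use of prohibited medication". The ET column of the extracted table shows no mark in these rows for anyone, so I do not count this as a further loss confined to this group.

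**Step 2: size for a mean outcome (assumed inputs).** Let p be the fraction of an arm removed and g the gap, in SD, between removed and retained participants. The full-arm mean is m − p·g and the retained mean is m, so removal shifts the arm mean by p·g. With 50 per arm, the standard error of a two-arm difference is √(2/50) = 0.20 SD.

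- One arm, p from 2% to 10% (1 to 5 people), g from 0.5 to 1.0: the shift runs from 0.02 × 0.5 = 0.01 SD to 0.10 × 1.0 = 0.10 SD, or 5% to 50% of the standard error.
- Two arms, 10% against 4%, g = 1 (5 against 2 people): 0.10 − 0.04 = 0.06 SD, or 0.06/0.20 = 30% of the standard error.
- Two arms, 20% against 4%, g = 1: 0.20 − 0.04 = 0.16 SD, or 80% of the standard error.

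Swapping the arms reverses the sign. Equal removal with equal gaps gives no shift in the difference.

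**Step 3: size for adverse-event incidence (assumed inputs).** If a fraction r of those removed would have had a first event after ET, then 100·p·r percentage points go uncounted in that arm. With p from 2% to 10% and r from 20% to 50%, this runs from 0.4 to 5.0 percentage points.

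**The case against.** There is a substantial case for leaving the rule alone.

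- Removal is permitted, not required. The illustration assumes that every user is removed, and its rates have no source in the documents.
- Use is already recorded. Section 6.5 requires every medication to be documented with indication, dates and dose, and Appendix A of the Stage 2 SAP reports prohibited medication as an important deviation by group. A reader might infer that use goes unrecorded, but it does not.
- Safety follow-up does not simply stop. ET retains vital signs, physical examination, laboratory tests, acuity, slit lamp, intraocular pressure and fundus examination, with ECG at selected sites. Adverse events leading to discontinuation (Sections 7.2 and 8.2), serious events and events of special interest (Section 8.2.3), and clinically significant laboratory values (Section 8.1.8) are all followed.
- Some triggers, such as contact lenses or cannabis, have no clear link to outcome. Artificial tears do not appear in the visible Stage 2 list in Section 6.5.4, and the related exception in exclusion criterion 2.01 is blacked out. Whether ordinary symptom relief triggers the rule cannot be determined.
- Efficacy is exploratory, Section 9.1 plans no hypothesis testing, and Appendix E of the Stage 2 SAP drops between-group tests of safety data.
- A drug given for worsening may close the 1 SD gap by Day 42, so continued visits would recover less than the illustration suggests.

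All of this limits the size of the concern. It does not remove it: later visits, new non-serious events and Day 42 outcomes that are never collected cannot be restored by analysis.

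**Conclusion.** The concern holds in a limited form. Followed as written, the plan can end observation of randomized participants for a reason that is sometimes related to outcome, and it sets no criteria for doing so. The loss is partial, and its frequency is unknown. The figure of 0.06 SD against a standard error of 0.20 SD rests wholly on assumed use of 10% against 4%, a 1 SD deficit and removal of every user. It indicates scale and is not an estimate.

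Three stronger readings are tempting and are not supported.

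- *That the vehicle arms are flattered.* The documents do not show which arms would use more prohibited medication. Section 6.3.2 cites ocular irritation and other reactions in 5% to 25% of Xiidra patients, so an imbalance could run the other way.
- *That type I error or power is affected.* There is no hypothesis test to affect, and the consequence is for descriptive and exploratory estimates.
- *That the plan lacks missing-data handling.* The efficacy methods of the Stage 2 SAP are not in the public text, so this cannot be judged.

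The change is worth making because it is cheap and prevents a loss that analysis cannot repair.

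**What to change.** In the Table 1-2 note and in Section 7.2, state that prohibited-medication use, already recorded and reported as a deviation, is not by itself a reason to end study participation. Ask these participants to continue the remaining scheduled safety and non-CAE assessments through Day 42, unless they withdraw consent or the investigator withdraws them for safety. Decisions on study intervention and on the CAE challenge stay with the existing medical judgement. Section 8.2.5 already takes a similar approach for pregnancy, where the participant may remain for follow-up through Exit.

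In the Stage 2 SAP, include all collected data in the Safety and ITT summaries, flag values after prohibited use, and add one supportive summary without them. That summary reintroduces the selection, so it should only be read beside the full one.

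The cost is a short amendment, a few visits already on the schedule and one extra summary. The downside is that some Day 42 values will reflect the added medication.

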2.1. Study Rationale

This is the FIH study to evaluate the safety, tolerability, PK, of AGN-242428 and AGN-231868 administered through topical ocular instillation. Data collected from animal studies suggest that both interventions have a good safety profile and the potential to reduce the signs and symptoms of DED. Data from this study will guide future development of either or both of these compounds for the treatment of DED.

2.2. Background

Inflammation plays a crucial role in the pathogenesis of DED. Therefore, an overarching approach to treating DED is to target the underlying inflammatory response that leads to epithelial damage and ocular symptoms such as dryness and discomfort. AGN-242428 and AGN-231868 are designed to reduce ocular inflammation associated with DED through 2 distinct mechanisms. Both interventions have favorable safety profiles and have been shown to be efficacious in nonclinical models. Xiidra was selected as the active comparator in Stage 2 because it is considered the current standard of care for the treatment of DED in the United States.

A detailed description of the chemistry, pharmacology, PK, efficacy, and safety of AGN-242428 and AGN-231868 is provided in the respective investigator's brochures. A detailed description of the chemistry, pharmacology, PK, efficacy, and safety of Xiidra can be found in the Xiidra package insert (Xiidra US package insert 2016).

2.2.1. AGN-242428

2.2.1.1. Pharmacology

RORγt is a nuclear hormone receptor that constitutively induces IL-17A gene expression. Inhibition of RORγt blocks the transcription of IL-23R, IL-17A, IL-17F, and IL-22, suppressing the IL-23 and IL-17 driven inflammation process. AGN-242428 is an inverse agonist (inhibitor) that binds in the ligand binding domain blocking the transcriptional activity of the receptor and suppressing cytokine production.

AGN-242428 is a potent and selective inhibitor of human RORγt. AGN-242428 inhibits the secretion of IL-17 from stimulated human peripheral blood mononuclear cells in serum-free media. This activity reflects the potential to modulate Th17-mediated responses that contribute to corneal barrier disruption and sustained disease observed in chronic DED. In vivo studies have demonstrated that AGN-242428 can prevent disease in experimental models of ocular allergy and autoimmunity that represent the cellular responses observed in chronic DED.

2.2.1.2. Pharmacokinetics

The ocular and systemic PK of AGN-242428 were characterized in rabbits. Following topical ocular administration of AGN-242428 to rabbit eyes, AGN-242428 concentrations in ocular tissues, including cornea, conjunctiva, and tears, were sustained above the anticipated efficacious levels for at least 12 hours postdose. Systemic exposure after a single dose of AGN-242428 in rabbits was minimal. Minimal (up to 2-fold) systemic accumulation of AGN-242428 was observed in the toxicokinetic studies after 42 days of dosing with AGN-242428 up to twice daily in the left eye and 4 times daily in the right eye in rabbits and dogs.

[figure not shown]
